PFC-Scale and PAPA MDD severity sum scores will be used to assess differences in depressive symptoms; HBQ and PAPA impairment scores will be analyzed to determine differences in functional impairment. Differences in emotion regulation (as an executive function) in the two groups will be examined using scores from the BRIEF-P; emotion development will be analyzed using scores from the ERC, Emotion Understanding, FACE, KIDSEDF, and the "Waiting" and "Puzzle" tasks. Post-assessment EDCl, BDI-II, and PSI scores will be compared between PCIT-ED and WL groups to determine differences in increases in Emotion Skill Learning and reduction of parental depressive symptoms and parenting stress.

Rates of remission (defined by 50% reduction in MDD severity and not meeting diagnostic criteria) will be compared in the PCIT-ED and WL subjects using logistic regression.

Interval assessment scores will also be analyzed across PCIT-ED and WL groups in repeated measures mixed models. In these models, repeated measures of PFC-Scale, HBQ MDD and externalizing co-morbidity severity and impairment, PSI and ESL (measured by EDCl) at pre-assessment, 6-week assessment, 12-week assessment, and post-assessment will be compared between the PCIT-ED and WL groups.

In addition to the analyses described above, pre-assessment variables that could possibly be associated with outcome, such as subject age and maternal depression, will be investigated as potential predictors of outcome.

Specific Aim 2: To investigate mediators and moderators of treatment effects.

Hypothesis 2A: Parental emotion skill learning (ESL) will mediate treatment effects. Child depression outcomes will be mediated by parental ESL.

Hypothesis 2B: Parental Emotional Intelligence (EI, a stable trait measured at baseline by MSCEIT) will be a moderator of ESL and child outcome. Parents with higher EI will show better ESL, and as a result, children of parents with high EI will show better outcomes than children of parents with low EI.

Analytic Approach: Parental ESL will be measured with the Emotion Development Coding instrument. This is an itemized assessment of parents' emotion skill learning. Each item is rated as 3=satisfactory, 2=needs practice, or 1=not evident. The total ESL score will be calculated as the mean of these items.

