estimates a moderation model with the effect of the independent variable on the dependent variable moderated by a proposed moderator variable. The independent variable (ESL score) and proposed moderator variable (pre-assessment parental EI) are centered to eliminate any multicollinearity effects. The macro generates the conditional effects of ESL score on the dependent variable (MDD severity sum score) at values of EI score equal to selected percentiles (e.g., 10th, 25th, 50th, 75th, and 90th percentiles) of the distribution in the sample. The Johnson-Neyman technique will be used to identify the values of EI score at which point the effect of ESL score changes from statistically significant to statistically non-significant. If EI score is found to be a significant moderator, the independent and moderator variables (ESL score and pre-assessment EI score) will be dichotomized so that all subjects fall into 1 of 4 categories (low ESL with low parental EI, low ESL with high parental EI, high ESL with low parental EI, and high ESL with high parental EI). Post-hoc pair-wise comparisons of treatment outcome in these 4 groups will be conducted.

Power for Moderation: To estimate power for this moderation analysis, a simulated dataset of 90 PCIT-ED subjects was created. This dataset contained variables for parental ESL, parental EI, and change in MDD severity sum score. Random data was generated for 45 “high EI” subjects and 45 “low EI” subjects assuming normally distributed data for each of these variables, with SD’s based on our pilot study (SD=0.22 for ESL, SD=15.6 for EI, SD=4.69 for MDD change score). The mean scores for the random normally distributed data varied in the two groups as we expect it to in the proposed study. For the “high EI” group, assumed means were 2.1 for ESL, 118 for EI, and -6.5 for MDD change. For the “low EI” group, assumed means were 2.5 for ESL, 99 for EI, and -1 for MDD change. Running the PROCESS macro on the simulated dataset yielded a significant interaction of ESL and EI, with a coefficient=0.2440 and SE=0.0758. Subtracting 1.96 from the corresponding t score (3.219) gave Z=1.259, which corresponds to power=0.90.

Specific Aim 3: To investigate whether reductions in depressive symptom severity and diagnostic remission is sustained 18 weeks after treatment has ended in those randomized to PCIT-ED first.

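### The moderation power simulation, as printed, gives high-EI parents the lower emotion skill score, contrary to Hypothesis 2B, and neither ordering of the means supports the stated power of 0.90

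*Combined protocol and SAP*

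**What the plan says.** Hypothesis 2B, under Specific Aim 2 of the SAP, reads: "Parents with higher EI will show better ESL, and as a result, children of parents with high EI will show better outcomes". The Analytic Approach that follows fixes the direction of the ESL scale: "Each item is rated as 3=satisfactory, 2=needs practice, or 1=not evident", and "The total ESL score will be calculated as the mean of these items". No reverse scoring is described, so a higher ESL score means better skill.

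For the Power for Moderation paragraph, "a simulated dataset of 90 PCIT-ED subjects was created", split into 45 high-EI and 45 low-EI parents, with "SD=0.22 for ESL, SD=15.6 for EI, SD=4.69 for MDD change score". The paragraph presents its means as the planners' expectation: "The mean scores for the random normally distributed data varied in the two groups as we expect it to in the proposed study". For high EI the "assumed means were 2.1 for ESL, 118 for EI, and -6.5 for MDD change"; for low EI the "assumed means were 2.5 for ESL, 99 for EI, and -1 for MDD change". The moderation model fitted to this dataset gave an ESL by EI coefficient of 0.2440 with SE 0.0758, from which the SAP derives a power of 0.90.

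**The concern.** The two parts of Specific Aim 2 disagree about which parents are expected to have the better skills. Hypothesis 2B gives the advantage to high-EI parents; the simulation gives it to low-EI parents, while still letting the children of high-EI parents improve more. In the scenario as printed, the first link of 2B (higher EI, better ESL) is reversed, and the second (better ESL, better child outcome) is reversed across the two groups as well.

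The 0.90 is the only power figure given for 2B. A reader cannot tell from the SAP whether the team expects the pattern in the hypothesis or the one in the simulation. The planned post-hoc comparison of four ESL-by-EI categories would be read against that unclear expectation.

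**Working it through.** **Inputs.** All come from Power for Moderation: ESL means 2.1 (high EI) and 2.5 (low EI); EI means 118 and 99; MDD change means -6.5 and -1; SDs 0.22, 15.6 and 4.69; 45 per group; interaction coefficient 0.2440, SE 0.0758. A negative change is an improvement.

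**The plan's own figure.** t = 0.2440 / 0.0758 = 3.219; 3.219 - 1.96 = 1.259; Phi(1.259) = 0.896, which rounds to the stated 0.90. The arithmetic from t to power is correct.

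**Size of the reversal.** ESL difference, high minus low EI: 2.1 - 2.5 = -0.4, and 0.4 / 0.22 = 1.8 SD in the wrong direction for 2B. Outcome difference: -6.5 - (-1) = -5.5, the direction 2B expects.

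**Implied correlations.** Assumption: no correlation within EI groups, since the SAP states none. For a 50:50 mix, total variance is the within-group variance plus the square of half the mean difference:
- ESL: sqrt(0.22² + 0.20²) = 0.297
- EI: sqrt(15.6² + 9.5²) = 18.26
- MDD change: sqrt(4.69² + 2.75²) = 5.44

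The between-group covariance is one quarter of the product of the mean differences:
- EI and ESL: 0.25 × 19 × (-0.4) = -1.9, so r = -1.9 / (18.26 × 0.297) = -0.35
- ESL and MDD change: 0.25 × (-0.4) × (-5.5) = +0.55, so r = 0.55 / (0.297 × 5.44) = +0.34

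Exchanging the ESL means turns these into +0.35 and -0.34, the signs that 2B implies.

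**Range for the assumption.** A common within-group correlation rho between EI and ESL adds rho × 0.22 × 15.6 = 3.432 × rho to the first covariance. At rho = 0.5 this gives (1.716 - 1.9) / (0.297 × 18.26) = -0.03; it reaches zero at rho = 1.9 / 3.432 = 0.55. Likewise, the second correlation reaches zero only with a within-group ESL to MDD-change correlation of -0.55 / (0.22 × 4.69) = -0.53.

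**Does the ordering drive 0.90?** I generated 20,000 datasets of 45 + 45 from the stated means and SDs, with independent draws within groups. Each was fitted by regressing MDD change on centred ESL, centred EI and their product, with a two-sided 0.05 test of the product term.

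| ESL means (high EI, low EI) | Mean interaction coefficient | Rejection rate | Datasets with absolute t of 3.219 or more |
|---|---|---|---|
| 2.1, 2.5 (as printed) | 0.000 | 4.7% | 0.16% |
| 2.5, 2.1 (exchanged) | 0.000 | 4.6% | 0.14% |

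The zero follows from symmetry. The two groups have equal size and equal SDs, so reflecting all three variables about their midpoints swaps the groups and leaves the joint distribution unchanged. The product of centred ESL and EI keeps its sign under that reflection while the outcome changes sign, so the population interaction must equal its own negative. This holds for any within-group correlation structure common to both groups. An ESL slope that differed between EI groups would create an interaction, but none is stated.

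**The case against.** The strongest reply is that this is a slip in the write-up. The 2.1 and 2.5 may have been transposed in the text while the simulation used them correctly, and the documents cannot exclude that. There is even a hint that the printed description is not exactly what was run: the reported SE is 0.0758, whereas the printed inputs give a mean SE of about 0.110, and a value as small as 0.0758 occurs in about 0.8% of simulated datasets. That stands. A reader might infer that 0.90 was computed in a scenario where 2B is false; the documents establish only that the printed inputs contradict 2B.

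A second reply is that the reversal has no bearing on the power of the interaction test. That also stands: the rejection rate is about 5% in both orderings. The 0.90 fails because it treats one dataset's t score as the true effect, and correcting the means would not repair that.

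A reader might also take the positive sign of 0.2440 as showing that skill helps less as EI rises. That is not supported. Under independent draws the sign is a coin toss, and 2B states no sign for the ESL by EI coefficient. Nor does the reversal contradict Hypothesis 2A, which concerns a path from treatment group through ESL across both arms; this simulation contains PCIT-ED subjects only.

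Finally, the overall sample size is developed in the simulation on multiple imputation earlier in the SAP, not here, and the planned moderation analysis itself is unaffected. That limits the weight of the point but does not remove the contradiction.

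**Conclusion.** The concern holds as an internal inconsistency; the arithmetic from t to 0.90 is right. As printed, high-EI parents are set 0.4 points (1.8 SD) lower on a scale where higher is better, against the explicit expectation in 2B, while the child-outcome means agree with 2B. The size of the reversal comes directly from the stated figures. The correlations of about -0.35 and +0.34 assume no within-group correlation; a common within-group EI to ESL correlation of about 0.5 would bring the first close to zero.

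Separately, the stated 0.90 is not supported in either ordering. This rests on independent draws, or a correlation structure common to both groups, since the SAP specifies no interaction. It matters for a secondary aim and should be corrected, but it does not touch the main treatment comparison.

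**What to change.** 1. Check the simulation code to see whether the ESL means were exchanged there or only in the text.
2. Reconcile Hypothesis 2B with Power for Moderation: correct the ESL means or, if the pilot really showed lower ESL in high-EI parents, rewrite 2B.
3. State the assumed ESL slope and an explicit ESL by EI interaction, with its sign, and any within-group correlations.
4. Rerun the simulation over many replicates, take power as the proportion of datasets that reject, and restate it in place of 0.90.

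The cost is one revised paragraph and a short re-simulation. The restated power may be less favourable than 0.90.

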To assess parental ESL as a potential mediator of the relationship between treatment group and child treatment response, a macro (for SAS or SPSS) developed by Hayes will be utilized. For mediation analyses, the PROCESS macro estimates path coefficients in a mediation model and generates bootstrap confidence intervals for the indirect effects of the independent variable on the dependent variable through a mediator variable. It is also possible to include covariates not proposed to be mediators in the model. Paternal ESL will be evaluated by entering post ESL score into the model as a potential mediator, with treatment group as the independent variable and change in PAPA MDD severity sum score as the dependent variable.

Power for Mediation: To estimate power for this mediation analysis, the following steps were taken. First, we expect the difference in MDD severity sum change score in the two groups to be approximately 2.5, with a SD of 4.69 (based on our pilot study). With 90 subjects per group, an alpha of 0.05, and a 1-sided test, power=0.97. Next, we expect the correlation of change in MDD severity sum score and ESL score to be approximately 0.25. Using Fisher's Z transformation with a sample size of 180, the correlation of 0.25 transforms to $Z = \tanh(0.25) * \sqrt{180-3} = 3.398$. Subtracting 1.96 gives 1.438, corresponding to power=0.92. Thus, we will be well-powered to detect a mediation effect.

To assess parental emotional intelligence (EI) as a potential moderator of treatment response, the PROCESS macro will be used. For moderation analyses, the PROCESS macro

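### The 90% power for the ESL by EI moderation test comes from one simulated dataset and does not follow from the inputs the plan states

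*Combined protocol and SAP*

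**What the plan says.** Under Specific Aim 2, Power for Moderation, "a simulated dataset of 90 PCIT-ED subjects was created", split into 45 high-EI and 45 low-EI subjects. Parental ESL, parental EI and change in MDD severity were generated "assuming normally distributed data for each of these variables", with SDs of 0.22, 15.6 and 4.69. Only the means are said to differ between the groups. For high EI, "assumed means were 2.1 for ESL, 118 for EI, and -6.5 for MDD change"; for low EI, "assumed means were 2.5 for ESL, 99 for EI, and -1 for MDD change".

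The result of one analysis follows: "Running the PROCESS macro on the simulated dataset yielded a significant interaction of ESL and EI, with a coefficient=0.2440 and SE=0.0758". Power is read from it directly: "Subtracting 1.96 from the corresponding t score (3.219) gave Z=1.259, which corresponds to power=0.90".

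The section gives no true interaction coefficient, no slope of MDD change on ESL by level of EI, no within-group correlation, and no replication of the simulation.

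**The concern.** There are two separate problems.

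1. **One draw is used as the truth.** Simulated power is the proportion of many datasets in which the test is significant. Here a single dataset was analysed and its t value was put in place of the non-centrality parameter. That t has a sampling error of about 1, which carries straight into the power figure.
2. **The described model contains no interaction.** Two groups that differ only in their means do not, by that fact, produce an ESL by EI product term. Whatever gave a coefficient of 0.2440 was either chance or something the plan does not describe.

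At stake is how Hypothesis 2B will be read. If the test is believed to have 90% power, a null result may be taken as evidence that EI does not moderate, when the plan gives no basis for that inference.

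**Working it through.** **Reproducing the plan's figure.** t = 0.2440 / 0.0758 = 3.219. Power = Φ(3.219 − 1.96) = Φ(1.259) = 0.896, which rounds to 0.90. The conversion is correct; the question is what went into it.

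**Precision of a single draw.** If the true non-centrality is anywhere in 3.219 ± 1.96, that is 1.259 to 5.179, power lies between Φ(1.259 − 1.96) = Φ(−0.701) = 0.24 and Φ(5.179 − 1.96) = Φ(3.219) = 0.999.

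**The interaction implied by the stated inputs.** Centre each variable at its overall mean. The group means are then ∓0.2 for ESL, ±9.5 for EI and ∓2.75 for MDD change (upper sign for high EI). Reversing the sign of all three variables swaps the two groups. With equal group sizes, equal SDs and the same correlations in both groups, the joint distribution is unchanged. The product ESL × EI keeps its sign under this reversal, while ESL, EI and MDD change all reverse theirs. The product is therefore uncorrelated with all three, and its population regression coefficient is exactly zero.

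**Standard error by hand, independence within groups.**
- Var(ESL) = 0.2² + 0.22² = 0.0884; Var(EI) = 9.5² + 15.6² = 333.61.
- Var(product) = 0.0884 × 333.61 − (0.2 × 9.5)² = 29.49 − 3.61 = 25.88.
- Var(MDD change) = 2.75² + 4.69² = 29.56. ESL and EI explain about 4.12 of this, leaving 25.44, a residual SD of 5.04.
- SE ≈ 5.04 / √(90 × 25.88) = 0.104. Simulation, which includes the finite-sample variation, gives a mean of 0.110.

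**Re-simulation.** 45+45 subjects, stated means and SDs; least squares of MDD change on centred ESL, centred EI and their product; two-sided 0.05; 20,000 to 40,000 replicates for most rows. Every structure below the first row is an assumption made here, not in the plan.

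| Structure within EI groups | Significant |
|---|---|
| Independent (mean coefficient 0.000, mean SE 0.110) | 4.6% |
| Same correlations in both groups (ESL–MDD, EI–MDD, ESL–EI, or all three) | about 4% to 5% |
| ESL–MDD +r high EI, −r low EI: r = 0.25 / 0.5 / 0.97 | 14% / 44% / 91% |
| EI–MDD −r high EI, +r low EI: r = 0.25 / 0.5 / 0.6 | 26% / 77% / 90% |
| Both of the above: r = 0.25 / 0.6 | 62% / over 99% |
| True interaction 0.2440 added, no within-group correlation, residual SD 4.69 | 60% |
| Same, residual SD reduced so the outcome SD stays near 4.69 | 61% to 62% |

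The 60% can be checked by hand: Φ(0.2440 / 0.1102 − 1.96) = Φ(0.254) = 0.60. Under independence a t of 3.219 or more occurs in about 0.07% of datasets.

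**The reported SE.** Under independence an SE of 0.0758 or less occurs in about 0.8% of datasets of 90, while the mean SE at n=180 is 0.0759. The Power for Mediation paragraph does work "with a sample size of 180, the correlation of 0.25 transforms to" its Z value. A wrong n is therefore one possible source of the small SE, but not a demonstrated one: a common ESL–MDD correlation of +0.5 at n=90 lowers the mean SE to 0.089 and makes 0.0758 or less a 16% event.

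**Direction of the ESL means.** Hypothesis 2B says "Parents with higher EI will show better ESL", yet the high-EI group is given 2.1 and the low-EI group 2.5, on an item scale where 3 is satisfactory. Swapping the two means leaves rejection at 4.6%, so this is a separate inconsistency and does not cause the power problem.

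**The case against.** The strongest reply is that the authors may have used a joint structure that they did not write down, and that 0.90 may be right under it. Such structures exist. With 0.244 as the true interaction at n=90, common within-group correlations move power well away from 60%: about 57% with ESL–MDD −0.25, 66% with +0.25, 77% with +0.5, and 90% with ESL–MDD +0.5 together with EI–MDD −0.5. The last case has a mean coefficient of about 0.244 and a mean SE of about 0.073, close to the plan's own output without any error in n.

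This stands, and it limits two things. The 60% is conditional on no within-group correlation and should not be quoted as the corrected power. The small SE is not proof that 180 subjects were used. It does not rescue the stated figure: that combination appears nowhere in the documents. The only ESL–outcome correlation given, 0.25, belongs to the mediation calculation with 180 subjects; used here as a common correlation without an added interaction, it still gives about 5%.

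A second reply is that the impact is modest: this is a secondary aim, and its interpretation will rest on the interaction estimate and the Johnson-Neyman region. That is fair on scope, but the power claim is still made and still unsupported.

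**Conclusion.** The concern holds. The power of 0.90 is one simulated t value converted to a probability, and the inputs beside it imply no interaction and a rejection rate of about 5%. This is not a finding that true power is 5%. The stated inputs do not determine power, which can lie between about 5% and nearly 100% according to a structure the plan leaves out. The zero interaction rests on equal group sizes, common SDs and the same within-group correlations in both EI groups; the first two are stated, and the plan gives nothing against the third. The defect is confined to the power statement for Hypothesis 2B and should be fixed. The enrolment calculation and Aim 1 do not depend on it.

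**What to change.** First retrieve the code behind the 0.90 and state in the SAP how the three variables were jointly generated and how many subjects were analysed. Then do one of the following:

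- Replace 0.90 with the proportion of significant results over many replicates at n=90, under an explicitly stated interaction and within-group correlations, with a range over plausible values.
- Withdraw the figure and label Hypothesis 2B exploratory, with no power claim.

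In the same edit, confirm or correct the 2.1 and 2.5 ESL means against Hypothesis 2B, and use one description of what EI moderates. Hypothesis 2B names ESL and child outcome, the Analytic Approach names treatment response, and the model described tests EI as a moderator of the effect of ESL on MDD severity. A treatment by EI term is needed only if the plan means to claim that EI moderates the treatment effect.

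The cost is a code check, a rerun simulation and some SAP wording. The restated power may be lower. No new data or change in sample size is needed.

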An intent-to-treat analytic approach will be employed. Multiple imputation will be utilized for subjects who discontinue during the study and do not complete the post-treatment assessment. Multiple imputation is desirable because instead of filling in a single value for each missing data point, each missing value is replaced with a set of plausible values, creating multiple imputed datasets. These datasets are then analyzed using standard procedures (that would be appropriate for a single, complete dataset), and results from the multiple data sets are combined into one set of results. The SAS procedures MI and MIANALYZE will be used for creating and analyzing multiple imputed data, resulting in statistically valid results that appropriately reflect the uncertainty due to missing values.

Multiple imputation is a useful method for analysis of datasets with data that are plausibly missing at random (MAR). Missing values rarely occur completely at random (MCAR). Instead, missing values are typically based on other variables, so they are MAR. During the multiple imputation process, the analyst should use all observed variables available in predicting missing values (even variables not used in analysis). If these variables are useful for predicting missing values, the multiple imputation increases power. Furthermore, by using an exhaustive set of predictor variables, the multiple imputation process creates a largely MAR dataset. Thus, multiple imputation can convert missing not at random (MNAR) data to MAR.

Simulation was used to determine sample size needed for analyzing multiple imputed datasets. We assume N=90 completers in each group, so a simulated dataset with N=180 subjects was created. Change in PAPA MDD severity sum scores were generated assuming normally distributed scores with a SD of 4.69 (pooled SD from our pilot RCT) and a mean difference in change scores in the two groups of 2.5. The demographic variables gender, age, race, family income, parental education level, and parental marital status were also included in this dataset. To simulate demographic characteristics, complete demographic profiles from the subjects in our pilot RCT were drawn with replacement 180 times and randomly assigned to the 180 simulated cases. A general linear model of change in PAPA MDD severity sum score by group was conducted for this simulated dataset.

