So, the relative increase in variance due to missing values is 32%, indicating that $1.32 * 180$ subjects = 238 subjects are required to attain the same power that would be attained in a sample of 180 subjects who all complete the study. In other words, 238 subjects must be enrolled in the study, with 180 completing, to achieve the same power when using multiple imputation as would be achieved if 180 subjects were enrolled and all completed. If multiple imputation were not used, and only complete cases were analyzed, approximately 238 subjects would have to be enrolled to produce 180 complete cases. Thus, multiple imputation is more efficient than complete-case analysis, in addition to avoiding bias due to MAR missingness.

A secondary analytic approach will be to use mixed models on non-imputed data. Mixed models can be used to analyze repeated measures data without discarding subjects with missing data. Mixed models will be used for measures only obtained at pre- and post-assessment and on measures with interval assessments. Analytic approaches for each set of specific aims and hypotheses are detailed below.

Specific Aim 1: To conduct an RCT of an early dyadic intervention for PO-MDD, PCIT-ED, compared to a WL control condition.

Hypothesis 1A: Compared to those randomized to the WL, preschoolers who are first randomized to PCIT-ED will show significantly increased rates of remission, greater reductions in MDD symptoms, and decreases in impairment.

Hypothesis 1B: Compared to those randomized to the WL, preschoolers who are first randomized to PCIT-ED will show significantly greater increases in emotional competence measured by the ability to accurately identify emotions in themselves and others and the ability to effectively regulate intense emotions.

Hypothesis 1C: Compared to those on the WL, parents who are first randomized to PCIT-ED will show significantly greater increases in emotion skill learning (ESL) and reductions in MDD symptoms and parenting stress.

Analytic Approach: Continuous post-assessment scores will be compared between PCIT-ED and WL groups using analysis of covariance, covarying for pre-assessment scores. The stratification variables, gender and externalizing comorbid diagnoses, will also be included as covariates in the models.

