Hypothesis 3: MDD remission (not meeting diagnostic criteria for ≥ 2 weeks) will be sustained at the 18 week follow-up in 80% of subjects who were in remission at the post-treatment assessment.

Analytic Approach: Rate of 18 week remission in subjects who met remission requirements at the post assessment will be calculated and compared to the 80% expected rate using a Chi-square goodness-of-fit test.

General Data Analysis Considerations: All outcome measures other than MDD diagnosis are continuous. The PFC-Scale and MDD severity scores from our pilot PCIT-ED and DEPI subjects were approximately normally distributed, as determined by the Shapiro-Wilk test. However, if these scores or other outcome scores are found to be from non-normal distributions, the data will be log- or power-transformed prior to analysis. Bonferroni correction will be used to limit the possibility of Type I errors for the main outcomes. A less conservative correction, such as the Bonferroni-Holm correction, will be applied for tests of other outcomes.

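### Aim 3 tests the predicted 80% sustained remission as its own null hypothesis, so agreement can rest only on a non-significant result, and no confidence interval is planned

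*Combined protocol and SAP*

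**What the plan says.** Specific Aim 3 asks whether reduced symptom severity and "diagnostic remission is sustained 18 weeks after treatment has ended in those randomized to PCIT-ED first". Hypothesis 3 puts a number on it: remission "will be sustained at the 18 week follow-up in 80% of subjects who were in remission at the post-treatment assessment".

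The Analytic Approach for Aim 3 is a single sentence with two parts. First, "Rate of 18 week remission in subjects who met remission requirements at the post assessment will be calculated". Second, that rate is "compared to the 80% expected rate using a Chi-square goodness-of-fit test".

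For Aim 3 the SAP gives no confidence interval, alternative rate, lower benchmark, margin, direction, alpha or power, and no rule for reading a non-significant result. The only confidence intervals named anywhere in the SAP are the bootstrap intervals for the mediation effect in Aim 2.

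**The concern.** A goodness-of-fit test against 80% has the null hypothesis that the true rate equals 80%, which is exactly what Hypothesis 3 predicts. The test can produce evidence against the prediction but none for it. Agreement could be inferred only from failure to reject, and failure to reject becomes more likely as the number of remitters falls or loss to follow-up rises. A smaller alpha has the same effect. The Bonferroni-type corrections under General Data Analysis Considerations, if they cover Aim 3, would therefore make apparent agreement easier to reach.

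If a non-significant result is reported as remission sustained as predicted, that statement could be made with a true rate about 10 points lower. Durability is one of three specific aims, and this is its only planned inference.

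A secondary ambiguity concerns who is counted. Hypothesis 3 describes remission as no diagnosis for at least 2 weeks. The Aim 1 Analytic Approach has "Rates of remission (defined by 50% reduction in MDD severity and not meeting diagnostic criteria", which adds a severity criterion. The Aim 3 sentence refers to remission requirements without naming either definition. The Hypothesis 3 wording most naturally governs, but the SAP does not say so.

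**Working it through.** The SAP gives no sample size, power or precision figure for Aim 3, so there is none to reproduce. The check asks how often the planned test would fail to reject 80% when the true rate is lower.

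**Inputs**
- Null rate: 0.80 (Hypothesis 3 and the Aim 3 Analytic Approach).
- Population: remitters in the PCIT-ED-first arm. The sample-size text says "We assume N=90 completers in each group", so on the plan's own assumption there are at most 90.
- Number of remitters: not stated. Assumed 27, 50 and 72, which are 30%, 56% and 80% of 90, all followed up. The case n = 90 is a ceiling that needs no assumed remission rate.
- Alpha: not stated for Aim 3. Assumed 0.05.

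**Non-rejection region.** With x children still in remission out of n, the 1-df statistic is

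X² = (x − 0.8n)² / (0.16n), not rejected if X² ≤ 3.84.

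For n = 50 the expected count is 40 and the half-width is √(3.84 × 0.16 × 50) = 5.54, so x from 35 to 45 is not rejected. The other regions are 18–25 (n = 27), 51–64 (n = 72) and 65–79 (n = 90).

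**Exact binomial probability of non-rejection**

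| True rate | n = 27 | n = 50 | n = 72 | n = 90 |
|---|---|---|---|---|
| 70% | 0.727 | 0.569 | 0.497 | 0.370 |
| 65% | 0.516 | 0.280 | 0.181 | 0.091 |
| 60% | 0.309 | 0.096 | 0.038 | 0.011 |

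**Number needed.** Power of 80% against a true 70% is first reached at 130 remitters (power 0.805). That exceeds the 90 completers. The SAP also says "238 subjects must be enrolled in the study, with 180 completing"; with equal arms that is 238 / 2 = 119 per arm, and 119 remitters would still leave 0.264 non-rejection at a true 70%.

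**Reading the hypothesis as at least 80%.** A significant result above 80% would then count as support. Its probability is:

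| True rate | n = 27 | n = 50 | n = 72 |
|---|---|---|---|
| 80% | 0.019 | 0.018 | 0.015 |
| 85% | 0.072 | 0.112 | 0.136 |
| 90% | 0.233 | 0.431 | 0.567 |

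A true rate at or near 80% would almost never be confirmed.

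**What an interval adds.** An observed 35/50 (70%) gives X² = (35 − 40)² / 8 = 3.125, which is not rejected. Its exact (Clopper-Pearson) 95% interval is 55% to 82% (Wilson 56% to 81%). An observed 40/50 gives X² = 0, with an exact interval of 66% to 90% (Wilson 67% to 89%).

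**Effect of a smaller alpha.** At an illustrative 0.025 with 50 remitters, non-rejection at a true 70% rises from 57% to 68%.

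**The case against.** The strongest reply is that the SAP nowhere says a non-significant result will confirm durability, so the harm depends on a reading it does not state. The rate will also be calculated, so it can be compared with 80% descriptively, and anyone with the count and denominator can compute an interval. On this view the gap is a reporting omission that can be repaired at publication, in a single-arm aim that leaves the randomized comparison untouched.

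Parts of this stand. The point estimate is planned, Aim 1 is unaffected, and the test usually catches large shortfalls: at a true 60% it rejects 90% of the time with 50 remitters, and 69% even with 27. The magnitudes depend on assumed numbers of remitters and an assumed alpha.

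It does not remove the problem. The one inference planned for Aim 3 cannot support Hypothesis 3 as worded, and without a stated rule, reading non-significance as agreement is left open. An interval computed after the fact does not settle in advance what the conclusion rests on. The ceiling of 37% at n = 90 needs no assumed remission rate.

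A narrower objection concerns the remedy. If the chi-square test is kept, an exact interval can disagree with it at the boundary: 34/50, 17/27 and 64/90 are all rejected, yet their exact 95% intervals include 80%. That is correct. The Wilson interval inverts this same test and avoids the mismatch.

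**Conclusion.** The concern holds: the analysis is wrong as written. The predicted 80% is the null of a non-directional test, inferential agreement with Hypothesis 3 can come only from non-rejection, and no interval for the rate is planned.

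The weakness is against moderate shortfalls. At alpha 0.05 with complete follow-up, a true 70% passes unrejected in about half to three quarters of trials with 72 down to 27 remitters, and in 37% at the ceiling of 90. Reading the hypothesis as at least 80% makes support possible in principle, but unlikely unless the true rate is well above 80%. The change should be made, though it affects only a single-arm follow-up aim. The two definitions of remission are a separate, lesser point that can be settled in the same edit.

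**What to change.** In the Aim 3 Analytic Approach:

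1. Keep the planned sustained-remission rate and report it with a 95% confidence interval, Wilson or exact. If the chi-square test is retained, use Wilson so that test and interval agree.
2. State that the durability conclusion rests on that interval, and that non-significance against 80% will not be read as confirmation.
3. State whether Hypothesis 3 means 80% or at least 80%.
4. Reconcile the Aim 1 and Hypothesis 3 definitions of remission in one sentence that names the definition used for both the Post 1 denominator and the 18-week outcome.

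A one-sided test against a minimum rate chosen and justified by the sponsor could be added, but the correction does not depend on it.

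The cost is SAP wording only, with no new data, visits or sample size. The downside is that a durability claim becomes harder to make: 40/50 would be reported as 80% with an exact interval of 66% to 90%, instead of as not different from 80%.
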